Specifically, we will test the hypotheses that:

(1) patients treated under a partial schedule of antihypertensive medication will show a greater amelioration of symptoms than that achieved by patients treated with that same (reduced) amount of drug administered under a continuous schedule of reinforcement;

Conditions permitting, we will also test the predictions that:

(2) irrespective of initial treatment regimen, relapse will occur more quickly following withdrawal of active medication in patients who do not continue to receive conditioned stimuli (placebo) than in patients who continue to receive conditioned stimuli; and

(3) when active drug is withdrawn and replaced by conditioned stimuli alone, resistance to extinction will be greater (i.e., rate of relapse will be less) among patients treated under a partial schedule of reinforcement than patients treated with the same amount of drug administered under a continuous schedule of reinforcement (the partial reinforcement effect).

b) Background

Rationale.

Because the proposed research represents a departure from any prior research, we provide here a brief description of the background and rationale for the strategies underlying the proposed experiment(s).

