Medication. Hypertensive patients will be treated with distinctively colored, *odored and flavored* gelatine capsules (Capsuline, Inc, Pompano Beach, FL) containing 12.5 mg (generic version, available from the Strong Memorial Hospital Research Pharmacy). The “placebo” will be a capsule containing 12.5 mg of an inert substance with the same characteristics as the active drug capsules. Capsules will be packaged in a blister strip of single application packets by the Investigational Drug Studies program in the Strong Memorial Hospital Research Pharmacy. Preparation of the sequence of medication would be done from coded patient numbers and would depend upon the schedule of reinforcement that was being used. For example, if one were imposing a 25% reinforcement schedule (only one fourth of the packets of capsules containing active drug), a random sequence would be constituted with the proviso that the patient would receive no more than two doses of consecutive placebo capsules. Randomization will be performed by the research pharmacy in blocks of eight. Allocation concealment will be guaranteed, since only the research pharmacist will be aware of group distribution and all other members of the research team will be blinded. He will provide the research nurse with the pre-labeled packages.

Length of study: 8 weeks for those subjects that complete the full set of procedures. For those subjects who relapse early, or whose blood pressure does not remit (10-point decrease for a period of 5 days) prior to the Exp 1 phase, the minimal period in the study is 3 weeks.

Exp 1: Baseline Period: 2 weeks after a screening physical examination that will be performed within one week of admission. ; Experimental Phase: 2 weeks (or less for subjects' whose mild hypertension relapses). Therefore, maximal possible period receiving carvedilol: 4 weeks.

Exp 2: 4 weeks. In this experiment subjects either receive placebo or no treatment. We expect the latter group to relapse after a few days. Those receiving placebo are hypothesized to relapse later, and we are assuming that will relapse before 4 weeks on placebo. However, if we find that there are subjects that after 4 weeks have not relapsed, we plan to continue the administration of the placebo until they relapse (beyond the 4 weeks). Because we believe that this will occur rarely, for practical reasons we will state in the consent form that this period may last “up to 4 weeks”.

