The choice of the β/α blocker for this study was based on:

a) targets receptors of the peripheral nervous system (PNS); it is a non-selective β -adrenergic blocking agent with alpha-1 blocking activity. It is approved for use in hypertension as well as heart failure. Other hypotensive drugs could have been chosen, however, their primary target is not “directly” aimed at the PNS or CNS. We are aware that ACE inhibitors decrease catecholamines, and angiotensin receptor blockers decrease vasopressin, however, for this initial study we chose a drug that is mostly associated to the sympathetic system. We believe that this will provide the best chances of success. Future studies will include alternative drugs.

b) Carvedilol has no adverse effect on glycemic control, and is the preferred β blocking agent for patients that have diabetes (as some of ours may).

c) We have preliminary published data (28) that strongly suggests the effectiveness of our conditioning paradigm in the pharmacotherapy of hypertension using a similar β blocker.

d) can be administered two times a day, leading to an enhanced number of “learned” exposures to the stimulus, and this regimen guarantees that subjects in groups that receive only one active drug

administration out of 4 will take adequate daily amounts of that will prevent them from the undesired rebound side effects of this medication that could occur if they were to have 3 days with no active drug.

Subjects will be started on the lowest recommended starting dose of 25 mg daily in 2 fractionated doses, which is reasonable given their level of hypertension (33,34). Once a reasonable blood pressure drop is achieved, they will be randomized to four experimental groups, as described in the methods section.

Potential participants will be informed that the purpose of the study is to determine if their blood pressure could be brought under control using lower amounts of medication and that, in the course of the study, the amount of medication they receive may be reduced. The medical staff with whom the patient comes in contact will not know if or when this occurs. Measurement of blood pressure during the study will be performed by the patients themselves, who will be instructed in the use of automated BP monitors (HEM-711AC, Omron Healthcare Inc., Bannockburn, IL) which will be provided. Subjects will obtain measurements twice (one after the other) in the AM and twice (one after the other) in the PM always at the same time of day.

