A screening physical examination will be performed within one week of admission into the study and only patients, who are in good health, display no contraindications for the use of beta blockers and disclaim the use of antihypertensive medication for at least 2 wk. before the start of the study will proceed to the initial maintenance or baseline period.

Patients will be excluded from participation if they use illicit drugs, were using anti-hypertensive medications within the previous 2 weeks other than ACE-inhibitors, angiotensin receptor blockers, calcium channel blockers, aldosterone antagonists, or diuretics **Patients will be excluded from participation if they use illicit drugs; they use inhalers regularly to control reactive airway diseases like COPD and asthma;** if pregnant or if sexually active women are not using contraceptives; if they cannot be followed or monitored appropriately; or renal insufficiency are determined, which may require a blood draw at the time of screening physical examination if subject has not had basic blood profile done in the past 12 months.

Experiment 1. Effects of a partial schedule of pharmacotherapeutic reinforcement in maintaining the therapeutic effects of in the treatment of hypertension.

The proposed research will determine if, capitalizing on conditioned pharmacotherapeutic effects, patients suffering from hypertension can be effectively treated with smaller cumulative amounts of a beta blocker, . Some patients in this initial experiment will be treated on a partial rather than a continuous schedule of pharmacologic reinforcement. These patients will be compared to: (a) patients that continue to be treated on a standard regimen of pharmacotherapy at the baseline dose, and (b) patients that receive the same (reduced) total amount of medication under a continuous schedule of reinforcement as that received by experimental patients being treated under a partial schedule of reinforcement, and another Dose Control Group that receives at the same dose and frequency as the Partial Reinforcement Group, but receives no interspersed exposures to the CS.

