It is possible that the therapeutic effects of a partial schedule of pharmacologic reinforcement (and, thus, a reduced amount of active drug) will be indistinguishable from a continuous (standard) regimen of pharmacotherapy. That outcome, however, is not critical for evaluating the role of conditioning in pharmacotherapies simply because these groups would have received different amounts of drug. Specifically, *it is hypothesized that patients treated under a noncontinuous schedule of medication will be less likely to show a recurrence of symptoms ("relapse") than patients treated with that same amount of drug administered under a continuous schedule of reinforcement.*

On the first visit, each potential subject will undergo a brief physical examination to record the medical history, sign an informed consent form, and receive instruction in the use of a blood pressure monitor. A strip of medication packets will be supplied at each clinic visit and will be taken by the subject at home, 2

times a day for the duration of the study.. The subject will return to the study center once a week or within 14 days of the drug dispensing cycle; this will allow flexibility for those with travel or work schedule challenges. The study coordinator will email or call to check on safety of the subject in the interim of a weekly clinic visit. Each drug card contains 15 days of study drug to ensure continual dosing in the event a weekly visit is missed. Packets containing medication will be dispensed by code so the patient and the physician will be blinded as to the nature of the medication. To consider the possibility that conditioning might be influenced by immediate stressful life experiences in these patients, we will examine this relationship using two measures of psychological distress administered at weekly intervals: the Hassles Scale, a frequently-used measure of daily stressors or “hassles” and the Impact of Events Scale (IES) (31).

The protocol for Experiment 1 is shown in Table 1. During a baseline period (of a maximum of 15 days), all patients will be treated BID with 12.5 mg. Those who satisfy the criterion of a 10-point decrease in blood pressure for a period of 5 days will be assigned randomly to experimental groups.

During the 15-day experimental period, the patients will be treated as follows:

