Patients in a **Standard Therapy Group** will continue to receive 100% of the dose of medication on the same reinforcement schedule (100%) as they received during the baseline (maintenance) period. (12.5 mg) would be taken 2 times daily for 15 additional days. This is a continuation of their standard pharmacotherapeutic maintenance regimen and constitutes one control group.

The **Partial Reinforcement Group** will be treated under a partial (25%) reinforcement schedule. That is, patients will receive the same dose of drug previously received, but only a quarter of the daily packets will contain active drug (12.5 mg); the remaining capsules will contain only an inert substance. Packets will be arranged to ensure that a patient never receives the “placebo” for more than two consecutive times. The selection of a 25% reinforcement schedule is based on the fact that we are using the minimum recommended starting dose of , and lower doses (particularly this much lower) are likely to have minimal if any pharmacologic effect. Therefore, the total daily dose of 6.25 mg. would not be sufficient to sustain the normotensive levels achieved under continuous reinforcement during the baseline period.

Dose Control Group-1, a control for the cumulative amount of drug received by the Partial Reinforcement Group, will be treated twice daily under a continuous (100%) reinforcement schedule, but each packet will contain only 25% of the active drug received during the baseline period.

To be sure that the reduced amount of drug received by the Partial Reinforcement Group is not sufficient by itself to lower blood pressure, a **Dose Control-2 Group** will receive the same active dose as the Partial Reinforcement Group but will not receive CSs on the intervening doses (6.25 mg once every other day).

Table 1. Experimental Protocol

GROUP	BASELINE PERIOD (15 days)			EXPERIMENTAL PERIOD (15 days)		
	Drug Dose*	Reinforcement Schedule**	Freq.	Daily Drug Dose***	Reinforcement Schedule**	Freq.
Standard Therapy	25	100	2xDay	25	100	2xDay
Partial Reinforcement	25	100	2xDay	6.25	25	2xDay

RSRB: 36447 12 V08.03.2016

Dose Control-1	25	100	2xDay	6.25	100	2xDay
Dose Control-2	25	100	2xDay	6.25	100	every other day

* Daily Dosage in mg of antihypertensive medication

** Percentage of treatment occasions when active drug is received

*** Average Daily Dosage in mg of antihypertensive medication

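### The Partial Reinforcement arm cannot have 25% active capsules and also never more than two placebos in a row; over 14 or 15 days, keeping the run limit gives it at least 29–33% more drug than Dose Control-1

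*Combined protocol and SAP*

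**What the plan says.** Section III.a, Medication, takes a 25% schedule as its example and requires that "a random sequence would be constituted with the proviso that the patient would receive no more than two doses of consecutive placebo capsules". The Experiment 1 text on the Partial Reinforcement Group then applies both rules to the arm itself. On the schedule it says "only a quarter of the daily packets will contain active drug (12.5 mg", and it says that packets are arranged so that placebo is never given "for more than two consecutive times". Table 1 gives the arm an average of 6.25 mg/day.

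DC-1 is the control for cumulative dose. It takes a capsule twice daily, and "each packet will contain only 25% of the active drug received during the baseline period", which also gives 6.25 mg/day in Table 1.

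Hypothesis 1 compares PR with patients given "that same (reduced) amount of drug administered under a continuous schedule of reinforcement". The introduction to Experiment 1 likewise describes controls who "receive the same (reduced) total amount of medication under a continuous schedule of reinforcement".

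The experimental period is 2 weeks under Length of study and 15 days under Experiment 1. On dispensing, the plan says "Each drug card contains 15 days of study drug".

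**The concern.** A limit of two consecutive placebos forces roughly every third capsule to be active, but a 25% schedule makes only every fourth one active. If both cannot hold, the pharmacist must break one written rule, and a reader of the results cannot tell which.

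The choice matters because PR against the dose controls is the principal analysis (Section III.c). The relapse power statement in Section II.b concerns groups 2 and 3, which in the order listed are PR and DC-1. The conditioning interpretation depends on these two arms receiving the same amount of drug. The protocol itself treats PR against Standard Therapy as not critical for judging conditioning because those arms receive different amounts. Extra drug in PR would act in the direction of Hypothesis 1, and the planned Cox and mixed models do not adjust for dose.

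**Working it through.** **Inputs.** Active capsule 12.5 mg, twice daily (Experiment 1, baseline period). PR schedule 25% active and placebo runs of at most two (Medication; Partial Reinforcement Group). DC-1 capsule 0.25 × 12.5 = 3.125 mg. Period 14 days = 28 capsules, or 15 days = 30 capsules.

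**The plan's own figure.** PR: 0.25 × 2 × 12.5 = 6.25 mg/day. DC-1: 2 × 3.125 = 6.25 mg/day. Both agree with Table 1, so the stated dose follows from the 25% schedule alone.

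**Can both rules hold?** With k active capsules there are k + 1 places for placebo runs (before, between and after the actives). Each holds at most two, so at most 2(k + 1) placebos fit. A sequence of n capsules therefore needs k + 2(k + 1) ≥ n, that is k ≥ (n − 2)/3.

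- n = 28: k ≥ 26/3 = 8.67, so at least 9 active (32.1%). With 7 active, 16 placebos fit and 21 are needed.
- n = 30: k ≥ 28/3 = 9.33, so at least 10 active (33.3%). With 8 active, 18 placebos fit and 22 are needed.

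An exact count of sequences confirms this:

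| Capsules | Active | Sequences, runs ≤ 2 | Sequences, runs ≤ 3 |
|---|---|---|---|
| 28 | 7 | 0 | 120 |
| 28 | 9 | 10 | – |
| 30 | 7 | 0 | 8 |
| 30 | 8 | 0 | 1,206 |
| 30 | 10 | 66 | – |

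There are also none with runs ≤ 2 at 8 of 28 or 9 of 30.

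**Dose if the run limit is kept (minimum).**

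- 14 days: PR 9 × 12.5 = 112.5 mg (8.04 mg/day); DC-1 28 × 3.125 = 87.5 mg (6.25 mg/day). Ratio 1.286, or +28.6%.
- 15 days: PR 10 × 12.5 = 125 mg (8.33 mg/day); DC-1 30 × 3.125 = 93.75 mg (6.25 mg/day). Ratio 1.333, or +33.3%.

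These minima require nearly fixed patterns. As an illustration under an assumed mechanism (each capsule drawn at 25% active, with an active one forced after two placebos), about 42.5% of capsules would be active. That is 0.425/0.25 = 1.70, or roughly 70% more drug than DC-1.

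**Dose if 25% is kept.** 7 of 28 gives 87.5 mg, equal to DC-1. 7 of 30 gives 87.5 mg and 8 of 30 gives 100 mg, each 6.25 mg (6.7%) away from 93.75 mg. Every one of these sequences contains a placebo run of three or more.

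**The case against.** The strongest reply is that 25% is plainly the design and the run limit only a packing detail. Table 1, the 6.25 mg/day figure and the repeated same-amount requirement all point that way. The plan also says that DC doses would be adjusted if the PR schedule were changed. On that reading the doses match and the principal contrast is not confounded. This is a fair guess at intent, but no sentence ranks the rules. The run limit is stated twice, once for this arm specifically, and the pharmacy's packing list is not in the documents.

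Second, the 29–33% applies to a full 14- or 15-day course. Patients who relapse leave early, and the minimum excess is then smaller: +14% over 7 days and +20% over 10 days. Both rules can hold together when n/4 ≥ (n − 2)/3, that is for n ≤ 8 capsules (4 days). This stands as a limit on the size. It does not help a strip that has to be packed for 14 or 15 days.

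Third, the protocol expects doses this low to have little or no pharmacologic effect, so 8.33 against 6.25 mg/day might matter little. The documents give no dose-response data to settle this either way. Dose Control-2 is aimed at the same worry but has only 10 patients. Its text regimen (6.25 mg every other day, averaging 3.125 mg/day) also does not agree with its 6.25 mg/day in Table 1, so it is a weak safeguard.

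Fourth, a limit of three placebos with 7 of 28 active is also fairly rigid: 21 placebos must go into eight places holding at most 24. Separate strips could also join into longer runs. Both points stand and are dealt with in the fix.

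**Conclusion.** The point holds. Over 28 or 30 capsules the two rules are incompatible, and this follows by counting with no distributional assumption. One of two things must happen. If the run limit is kept, PR receives at least 28.6% (14 days) or 33.3% (15 days) more drug than DC-1 over a full course, in favour of the hypothesis. If 25% is kept, the doses match exactly or to within 6.7%, and the stated run limit is broken with no replacement.

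This rests on reading the limit as capsules rather than days, which is what the Medication text says. The size of any bias in relapse cannot be derived from the documents. It should be corrected all the same, because equal dose is the condition that gives the PR against DC-1 comparison its meaning.

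**What to change.** **Preferred.** Keep the 25% schedule and change the limit, in both places, to at most three consecutive placebo capsules.

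- Settle on one period length and fix the number of active capsules per patient. With 28 capsules, 7 active matches DC-1 exactly. If the 15-day card is kept, use 8 of 30 (100 mg, 6.67 mg/day) and set DC-1 to 100/30 = 3.33 mg per capsule.
- Apply the limit to each patient's whole sequence, across strips, so that replacing a card does not create a longer run.
- With 12-hourly dosing, three placebos between actives put active doses at most 4 × 12 = 48 hours apart. This is inside the plan's own concern about "rebound side effects of this medication that could occur if they were to have 3 days with no active drug".

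**Alternative.** Keep the two-placebo limit and adopt a one-third schedule (10 of 30, 125 mg). Raise DC-1 to 125/30 = 4.17 mg per capsule (8.33 mg/day), and re-derive Dose Control-2 to match.

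**In either case.** Report cumulative milligrams dispensed by arm. If the optional 15% schedule is used, give it its own run limit: with 4 or 5 active of 30, the longest placebo run is at least 6 or 5 capsules (3 or 2.5 days).

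**Cost.** Protocol wording and a regenerated packing list, plus a new DC-1 capsule strength unless 7 of 28 is used; no extra patients or visits. The preferred fix allows one more consecutive placebo (48 rather than 36 hours between active doses) and, at 7 of 28, leaves 120 possible sequences. The alternative raises the reduced dose slightly and leaves only 66.

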b) Number of Subjects: 121. Sample size and Power Analysis: The proposed study will recruit 37 subjects for each of the ST, PR and DC1 treatment conditions, and 10 subjects for the CD2 group. The study has 93% power to detect a 50% difference in relapse rate between group 2 and group 3 over the 2-week assessment period, even account for 10% dropout rate based on a two-sided $\alpha = 0.05$ using the method of Lakatos, E. (35). We selected a 50% relapse rate difference for the power calculation based on our prior experience. For the primary continuous symptom measure blood pressure, we have 80% power to detect about a medium effect size 0.56 based on a longitudinal study design with 7 assessment points, a conservative estimate of within-subject correlation 0.5, and a two-sided type I $\alpha=0.05$ using the method of Tu et al. (36). Note that although blood pressure is assessed twice daily in Experiment 1, we conservatively set the number of assessments at 7 to improve the robustness of the power estimates. Thus, the proposed sample size not only has sufficient power to detect a clinically meaningful difference in relapse rates, but also to find meaningful change patterns for blood pressure over the treatment course.

c) Sex of subjects: The male to female ratio will follow the distribution of hypertension in the Rochester area community. Pregnant or nursing females will be excluded due to the nature of the intervention (carvedilol is Category C). Females of child bearing potential will be required to use 2 birth control methods during the study in order to participate.

d) Age of Subjects: 18 to 80 years of age. Carvedilol is not intended for use in children.

e) Racial and Ethnic Origin: No restrictions. It will follow the distribution of patients seen in the Rochester area.

f) Vulnerable Subjects: None will be enrolled.

III. METHODS AND PROCEDURES

a) **Study Design.** Randomized, single blind.

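### Allocation concealment is called guaranteed, but for Dose Control-2 the stated reason does not hold: its regimen is visible and the fixed block of eight is printed, so staff could sometimes rule that arm out for the next patient

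*Combined protocol and SAP*

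**What the plan says.** All references are to the combined protocol and SAP.

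- **Randomisation and concealment** (III a, Medication): "Randomization will be performed by the research pharmacy in blocks of eight. Allocation concealment will be guaranteed, since only the research pharmacist will be aware". The reason in full is "since only the research pharmacist will be aware of group distribution and all other members of the research team will be blinded". Of the pharmacist it then says: "He will provide the research nurse with the pre-labeled packages".
- **Pack form** (same paragraph): "Capsules will be packaged in a blister strip of single application packets". Experiment 1 adds that each card covers 15 days.
- **DC-2 regimen** (Experiment 1): the group "will not receive CSs on the intervening doses (6.25 mg once every other day". Table 1 lists every other day for DC-2 and twice daily for Standard Therapy (ST), Partial Reinforcement (PR) and Dose Control-1 (DC-1).
- **Staff contact**: the Schedule of Events has study agent dispensed and the diary reviewed weekly.
- **Blinding label** (III a): "Randomized, single blind".
- **Point of randomisation**: the rationale for the drug says "Once a reasonable blood pressure drop is achieved, they will be randomized to four experimental groups". Experiment 1 gives a definite criterion, a 10-point fall in blood pressure for 5 days, within a baseline of at most 15 days.
- **Role of the comparison** (III c): PR against each of DC-1 and DC-2 is the principal analysis. Section II b) plans 37 patients in each of ST, PR and DC-1, and 10 in DC-2.

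**The concern.** The guarantee rests on everyone except the pharmacist being blind. DC-2 cannot be hidden in that way. A matching dummy capsule is the conditioned stimulus, which is exactly what this arm must not receive. Staff who hand over the packs or go through the diaries would see the difference.

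This goes beyond unblinding after assignment. If past DC-2 assignments are visible and the block length is known, some future places can be deduced before the patient is randomised. Once a block's DC-2 places are used, the rest of that block cannot be DC-2. Once only DC-2 places remain, the next patient must be.

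A patient reaching the end of the run-in could then be randomised sooner, later or not at all according to what the next place can be. That would make the DC-2 patients differ from the others for reasons other than chance. With 10 patients planned in DC-2, a few steered assignments would matter to PR versus DC-2.

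**Working it through.** **Plan's own total.** 3 × 37 + 10 = 121, as stated in II b).

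**Is DC-2 visible?** Twice daily for 15 days is 2 × 15 = 30 capsules. Every other day for 15 days is 7 or 8. The opening of Experiment 1 describes DC-2 as having PR's dose and frequency without the interspersed stimuli, which gives 25% of 30 = 7.5. Either description leads to about 7 to 8 against 30. The DC-2 pack itself is not described, so recognition is inferred from the regimen. Even an opaque pack would need an every-other-day instruction. ST, PR and DC-1 share the twice-daily schedule, and nothing in the documents makes them distinguishable.

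**Does a block of eight fit the arm sizes?** 121/8 = 15.125 blocks. The planned ratio would need 8 × 37/121 = 2.45 places for each large arm and 8 × 10/121 = 0.66 for DC-2. With the three large arms equal and all four arms present, 3k + m = 8 allows only 2:2:2:2 or 1:1:1:5. Two DC-2 per block would give 2 × 15.125 ≈ 30 DC-2 patients, and one per block about 15, against 10 planned. One per block also leaves 7 places, which do not split equally among three arms. The composition is therefore unknown, and both cases below are assumptions for illustration.

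**How much could be deduced?** Assume that only DC-2 is recognisable and that staff track block boundaries. For a permuted block of size B with d DC-2 places:

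- expected places after the last DC-2 (certain not DC-2): (B − d)/(d + 1)
- expected places when only DC-2 remains (certain DC-2): d/(B − d + 1)

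| B = 8 | Certain not DC-2 | Certain DC-2 | Total known | Known to be DC-2 |
|---|---|---|---|---|
| d = 2 | 6/3 = 2.00 | 2/7 = 0.286 | 2.286/8 = 28.6% | 0.286/8 = 3.6% |
| d = 1 | 7/2 = 3.50 | 1/8 = 0.125 | 3.625/8 = 45.3% | 0.125/8 = 1.6% |

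Full enumeration of the placements gives the same results.

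**Comparator.** In one unblocked list of 121 with 10 DC-2 places, the expected number after the last DC-2 is 121 − 10 × 122/11 = 10.1, or 8.3% of places.

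**If DC-2 closed at 10.** This would happen after 5 blocks (40 patients) with two per block, or 10 blocks (80 patients) with one. The remaining 81 or 41 patients would then be known not to be DC-2. The plan describes no such change of composition.

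**The case against.** The strongest reply is that foreknowledge needs three things the plan does not supply: the number of DC-2 places per block, the block boundaries, and staff who keep count. This stands, and it makes the percentages conditional. They should not be scaled to 121 patients, because the implied 30 or 15 DC-2 patients contradict the planned 10.

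Second, most of what could be known is only that the next patient is not DC-2: 2.00 of 2.286 places (87.5%) or 3.50 of 3.625 (97%). At 10/121, not DC-2 is already the expectation about 92% of the time. Nobody could steer a patient into PR in particular. This also stands.

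Third, the gate is tighter than the loose phrase suggests. That sentence refers on to the methods, where the criterion is numeric, and readings come from patients' automated monitors. At the projected 40 patients a year, one is randomised about every 365/40 = 9 days, so about 15/9 = 1.6 future randomised patients are in run-in at once. Swapping patients would seldom be practical. This stands in part. Delaying or withholding one patient remains possible, and nothing requires the criterion to be recorded as met before the assignment is released.

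A reader might also infer from the label "Randomized, single blind" that staff know every arm. The documents do not support that. The Medication paragraph, the information given to participants and the dispensing text in Experiment 1 all say that staff or the physician are blinded. The label conflicts with them and needs reconciling, but it is not evidence that all allocations are known.

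**Conclusion.** The claim of guaranteed concealment is not supported for DC-2, because past DC-2 assignments are very probably identifiable and the block size is fixed and printed. Under the two illustrative compositions, DC-2 status would be certain in advance for about 29% to 45% of places, nearly all of it as not DC-2. This rests on recognition of DC-2 and on staff tracking the blocks. No resulting bias in the relapse comparison can be calculated from the documents.

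A reader might go further and conclude that concealment fails for the trial, or that staff routinely know the next assignment. Neither follows. Concealment is weakened for DC-2 only. The exposure is at the randomisation gate and concerns PR versus DC-2. PR versus DC-1, the contrast to which the stated 93% power appears to refer (group 2 versus group 3), is not affected by this mechanism. The point is still worth acting on, because PR versus DC-2 is named as principal and the change is cheap.

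**What to change.** 1. Require the Experiment 1 criterion (10-point decrease for 5 days) to be recorded as met before the pharmacy releases an assignment, and make the looser phrase in the drug rationale refer to it. This is the most useful step, since it limits steering even though DC-2 stays visible.
2. Replace the fixed block of eight with a pharmacy-held list of undisclosed, varying block sizes that approximates 37:37:37:10, and remove the block size from the protocol that staff hold. A ratio of about 4:4:4:1 comes close: 121/13 = 9.3 sets give about 37 per large arm and 9 in DC-2. Larger blocks alone would not help. A fixed, known block of 13 with one DC-2 gives (12/2 + 1/13)/13 = 46.7% of places known. The gain comes from staff not knowing where a block ends.
3. Replace the guarantee with a statement that DC-2 is recognisable after assignment and that concealment rests on steps 1 and 2. Describe the DC-2 pack, and reconcile the single-blind label with the text on staff blinding.

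The cost is a few protocol sentences, a new pharmacy list and slightly looser balance between arms, with no extra patients or staff. One limit remains: once the tenth DC-2 place is filled, later patients are known not to be DC-2 under any scheme that keeps to the printed arm sizes.
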